1.9.2 Open-Label Extension

Primary endpoints for the OLE include cerebral amyloid imaging using [¹¹C]PiB-PET as well as the safety and tolerability of treatment with gantenerumab at higher doses.

Additional study endpoints for the gantenerumab OLE will be specified in the gantenerumab-specific SAP. The objectives of the OLE are as follows:

- (i) To enable participants, who have committed as much as 4 to 7 years to the double-blind treatment period of the study, to continue or begin to receive gantenerumab, which improves critical markers of their progressive disease, following their participation in the longest placebo-controlled trial in DIAD;
- (ii) To determine if continued treatment with gantenerumab at its target dose can result in complete removal of brain amyloid;
- (iii) To investigate which non-amyloid related downstream biological measures (e.g. tau and markers of neurodegeneration) can be improved or normalized with complete removal of amyloid at different stages of disease;
- (iv) To investigate the relationship of these biological measures with cognitive and clinical findings; and
- (v) To assess the summation of gantenerumab's effect on biomarkers during the entire double-blind period and open label extension period, including the common close portion in which biomarkers were not assessed (i.e., from year 4 to 7).

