4.1.2 Biomarker Endpoint Power Analysis

Based on DIAN-TU-001 data from the double-blind period, the mean (SD) change from the OLE baseline in PiB-PET composite SUVR to the end of the 3-year OLE period with dosing up to CCI [REDACTED] CCI [REDACTED] is projected to be at least -0.473 (0.540) for participants on gantenerumab from the beginning of the double-blind period, and participants starting gantenerumab in OLE (having been on either active solanezumab or placebo) together. The recruitment goal of OLE is to enroll 60 to 90 of the 144 mutation positive participants who participated in the placebo-control period. Assuming an annual dropout rate of 5%, at the end of 3-year OLE, there will be 51 to 77 participants and it will provide over 99% power to detect the projected mean change from baseline using a one-sided one-sample t-test with type I error 0.025.

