2. STUDY OBJECTIVES

2.1. PRIMARY OBJECTIVE

The primary objective for the final analysis of the Open Label Extension (OLE) is to determine if continued treatment with gantenerumab at its target dose can result in continued or complete removal of brain amyloid plaque using cerebral amyloid imaging using [¹¹C]-Pittsburgh Compound B (PiB) amyloid PET imaging tracer ([¹¹C]PiB) Positron emission tomography (PET).

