16.1.3. PRIMARY ANALYSIS OF PRIMARY EFFICACY VARIABLE(S)

The primary objective for the OLE is to determine if treatment with gantenerumab at its target dose can result in removal of brain amyloid plaque using cerebral amyloid imaging using [11C]PiB-PET.

The primary efficacy analysis will be performed for the OLE Gant mITT without the use of controls in the model. A Mixed-Effects MMRM analysis will be used to test if the change from the OLE baseline to the end of OLE in PiB-PET SUVR is significantly less than 0 for the OLE Gant mITT population. The MMRM will include the OLE baseline PiB-PET SUVR and visit (treated as categorical) as the fixed effects. An unstructured variance-covariance matrix will be

Author: [REDACTED]

Version Number:

7

Version Date:

07Dec2023

Template No.: CS_TP_BS016 Revision 6

Reference: CS_WI_BS005

Effective Date: 02Dec2019

used to model the within-subject errors among the repeated measures. If the unstructured covariance structure matrix results in a lack of convergence, the following covariance structures will be assumed in sequence: heterogeneous Toeplitz, heterogeneous autoregressive, heterogeneous compound symmetry, and compound symmetry. The corresponding p-value and the 95% confidence interval for the estimated least squares mean change at each visit will be presented. If the upper bound of the 95% CI at the year 3 OLE visit is less than 0, it is concluded gantenerumab significantly removes amyloid plaque at year 3. In the case that a structured variance-covariance matrix is used to enable the model to converge, the "sandwich" estimator of the variance-covariance matrix will be employed by using the "empirical" option in the proc mixed procedure. P-values for within-subject change resulting from a one-sample t-test using least squares mean estimates and associated standard errors will be presented.

Descriptive statistics including number of observations, mean, SD, median, minimum, and maximum will be provided by visit. P-values for within-subject change resulting from a one-sample t-test using least squares mean estimates and associated standard errors will be presented. In addition, a listing of the primary endpoint will be presented.

Figures of model estimated mean over time or spaghetti plots of individual data over time/EYO color-coded by treatment arms and doses will be presented as deemed necessary by Washington University team and may be included in CSR as needed.

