16.1.4.3. Gantenerumab Treatment Effects during the Whole Study Duration (Double-Blind + OLE)

To evaluate the treatment effect of gantenerumab during the whole study duration, the change from the double-blind baseline for subjects in the All Gant exposure mITT and for subject in the OLE Gant All Gant exposure mITT will be calculated for each post double-blind baseline visit and will be analyzed using the MMRM model (without controls) described in [Section 16.1.3](#). The MMRM model will include the double-blind baseline value, the double-blind treatment arm (gantenerumab, solanezumab, placebo) as applicable per analysis population, visit, and the interaction between the double-blind treatment arm and visit as the fixed effects. The visit variable will be considered as categorical with the following categories: visit 1 (the ~1-year visit in the double-blind period), visit 2 (the ~2-year visit in the double-blind period), visit 3 (the ~4-year visit in the double-blind period), visit 4 (the OLE baseline visit), visit 5 (the ~1-year OLE visit), visit 6 (the ~2-year OLE visit), visit 7 (the ~3-year OLE visit). Subjects on gantenerumab or placebo during the double-blind period will contribute to all visits. Subjects on solanezumab during the double-blind period will not contribute to post-baseline values within the double-blind period. An unstructured variance-

covariance matrix will be used to model the within-subject errors among the repeated measures. If the unstructured covariance structure matrix results in a lack of convergence, the following covariance structures will be assumed in sequence: heterogeneous Toeplitz, heterogeneous autoregressive, heterogeneous compound symmetry, and compound symmetry. In the case that a structured variance-covariance matrix is used to enable the model to converge, the "sandwich" estimator of the variance-covariance matrix will be employed by using the "empirical" option in the proc mixed procedure.

The corresponding p-value for the difference from no change from baseline and the 95% confidence interval for the estimated least squares mean change at each visit will be presented.

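### The stated primary objective concerns continued gantenerumab, but no planned model formally tests OLE amyloid change in participants already on it

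*SAP*

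**What the plan says.** **Objective.** SAP 2.1 sets out to "determine if continued treatment with gantenerumab at its target dose can result in continued or complete removal of brain amyloid plaque". Protocol Appendix 3, section 1.9.2, objective (ii), is similar: "To determine if continued treatment with gantenerumab at its target dose can result in complete removal of brain amyloid". SAP 16.1.3 restates the aim without the word continued: "The primary objective for the OLE is to determine if treatment with gantenerumab at its target dose can result in removal of brain amyloid".

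**Primary analysis.** The population is the OLE Gant mITT, which SAP 5.3 defines without regard to double-blind treatment. On the model: "The MMRM will include the OLE baseline PiB-PET SUVR and visit (treated as categorical) as the fixed effects". There is no term for double-blind arm. The rule is "If the upper bound of the 95% CI at the year 3 OLE visit is less than 0", in which case gantenerumab is said to remove plaque significantly at year 3.

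**Hypothesis and sizing.** Protocol Appendix 3, section 4.1.1, states the null hypothesis for everyone who enters the OLE. Section 4.1.2 projects one mean change, -0.473 (SD 0.540), for those on gantenerumab since the double-blind period and "participants starting gantenerumab in OLE (having been on either active solanezumab or placebo) together".

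**Supplementary analyses by prior arm.**
- SAP 16.1.4.1 compares the former gantenerumab group's double-blind change with the OLE change of the former solanezumab and placebo groups.
- SAP 16.1.4.3 includes double-blind arm and its interaction with visit, but analyses "the change from the double-blind baseline for subjects in the All Gant exposure mITT" and for the population treated with gantenerumab in both periods.
- SAP Table B (section 17) gives the aim of 16.1.4.1 as comparing the effect during the OLE by double-blind treatment.

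**The concern.** Two kinds of participant are averaged in the primary estimate: those continuing gantenerumab and those receiving it for the first time. Their expected changes may differ. Protocol Appendix 3, section 1.4, reports that gantenerumab significantly lowered PiB-PET against placebo at double-blind years 2 and 4, so the continued group may have less amyloid left to clear. A pooled fall can therefore come wholly from first-time starters.

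The planned analyses do not separate the two for the period that matters. In 16.1.4.1 the continued group contributes no OLE data, which does not match the aim in Table B. In 16.1.4.3 each p-value is against double-blind baseline, so a fall achieved before the OLE counts towards the Year 3 result. The exposure model in 16.1.4.5 has no prior-arm term. By contrast, SAP 16.2.4.1.2 does split the OLE population by double-blind arm for CDR-SB. At stake is whether the trial can answer the question in SAP 2.1.

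**Working it through.** **Inputs.** Mean -0.473, SD 0.540, enrolment 60 to 90, dropout 5% a year, one-sided 0.025 one-sample t-test (Protocol Appendix 3, 4.1.2). Double-blind arms: 52 gantenerumab, 52 solanezumab, 40 placebo (Protocol 3.3). The OLE split by prior arm is not given; 52/144 = 36% serves as a proxy, with a range of 25% to 50%.

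**Reproducing the plan.** Completers: 60 × 0.95³ = 51.4 and 90 × 0.95³ = 77.2, matching 51 to 77. Exact power (noncentral t) at n = 51 is above 99.9% for -0.473 and 81.4% for -0.22. Both agree with the protocol (over 99%; more than 80%).

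**Pooled test when the continued group does not change.** Let p be the continued share, with starters at -0.473 and the continued group at 0.

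- Pooled mean = (1 − p) × (−0.473). At p = 0.361: 0.639 × (−0.473) = −0.302.
- SD: either 0.540, or the mixture SD √(0.540² + p(1 − p) × 0.473²). At p = 0.361 this is √(0.2916 + 0.0516) = 0.586.

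Probability that the primary rule is met (mixture SD to SD 0.540):

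| Continued share | Pooled mean | n = 51 | n = 77 |
|---|---|---|---|
| 25% | -0.355 | 99.0% to 99.6% | above 99.9% |
| 36% | -0.302 | 95.1% to 97.5% | 99.4% to 99.8% |
| 50% | -0.236 | 80.2% to 86.6% | 93.5% to 96.7% |

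**Variations at the 36% share.**
- The continued group gains 0.10: pooled mean 0.361 × 0.10 − 0.302 = −0.266; success 86.7% to 93.2% (n = 51) and 96.7% to 99.0% (n = 77).
- The pooled mean is exactly the projected -0.473 but comes only from starters (−0.473/0.639 = −0.740): success 99.9% or more.

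**Does the OLE baseline covariate prevent this?** A simulated Year 3 ANCOVA was run with 2,500 runs per setting. It assumed baseline SD 0.8, slope -0.2, and an OLE-baseline gap between groups of 0 to 1.0 SUVR. Pooled success was 97.3% to 97.6% (n = 51) and 99.7% to 99.8% (n = 77). The covariate does not prevent it.

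**With an arm-specific estimate.** In the same simulation, testing the continued group alone succeeded in 2.5% to 3.4% of runs when its true change was 0. At a 36% share there are about 18 (of 51) to 28 (of 77) continued completers. One-sample power is 93.8% to 99.4% for -0.473 and 37% to 55% for -0.22. The 95% half-width is 2.110 × 0.540/√18 = 0.27 to 2.052 × 0.540/√28 = 0.21, against 2.009 × 0.540/√51 = 0.15 to 1.992 × 0.540/√77 = 0.12 for the pooled mean.

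**The case against.** The strongest reply is that pooling is the plan's declared hypothesis. The protocol null, the sizing and SAP 16.1.3 all concern everyone in the OLE, so the test matches what it claims to test. This stands. A reader might infer that the primary analysis is invalid or wrongly modelled; the documents do not support that.

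Continued could also mean sustained OLE dosing. Everyone restarts titration (Protocol Appendix 3, 2.2), and the section 1.5 headings give the OLE regimen (1500 mg Q2W) as higher than the double-blind one (1200 mg Q4W). This partly stands. However, objective (i) in section 1.9.2 separately mentions continuing and beginning gantenerumab, so the natural reading of objective (ii) is the continuing group.

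By-arm information is not absent. Section 16.1.4.3 yields least squares means for the continued group at OLE baseline (visit 4) and OLE Year 3 (visit 7), and SAP 5 lays tables out by double-blind arm. This stands. What is missing is a named contrast between those visits, or an arm-specific estimate from OLE baseline.

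The illustration gives starters alone a projection made for both groups together, and borrows the double-blind share. That is fair: it shows what the rule permits, not what is expected.

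**Conclusion.** The point holds as a gap between the stated objective and the planned tests. The pooled test is sound for the pooled hypothesis but cannot by itself support a conclusion about continued treatment. Under the stated assumptions it would succeed with probability about 80% to 99.6% at n = 51 even if the continued group did not change, and about 95% to 97.5% at the 36% share.

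Two further readings are tempting and go too far. One is that a pooled success would be reported as continued removal; the rule in 16.1.3 says only that gantenerumab removes plaque. The other is that omitting prior arm costs material precision. Even in this scenario, accounting for arm lowers the SD from 0.586 to 0.540, about 8%, and planned power already exceeds 99%.

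The completer numbers assume a full three-year OLE. The SAP version 7 revision history records early termination, so Year 3 data may be sparser than this; the documents do not say by how much. This is a low-cost improvement, not a flaw in the primary test.

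**What to change.** 1. Keep the pooled Year 3 test in 16.1.3 as primary.
2. Add a supplementary run of that model with double-blind arm (gantenerumab vs solanezumab/placebo) and arm-by-visit, reporting the Year 3 least squares mean change from OLE baseline with 95% CI for each arm. Alternatively, prespecify the visit 7 minus visit 4 contrast for the gantenerumab arm in 16.1.4.3.
3. Reconcile the text of 16.1.4.1 with its aim in Table B.
4. State that any claim about continued removal rests on the gantenerumab-arm estimate.

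The cost is SAP wording and one supplementary output, with no new data. The arm intervals will be wider, and a small continued effect may go undetected, so the interval should be reported rather than only a p-value. An unstructured covariance with arm-by-visit terms may be hard to fit if few Year 3 scans exist; the fallback structures in 16.1.3 can apply. Because the analysis is added after the interim, it should be labelled supplementary.

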16.1.4. SUPPLEMENTARY ANALYSIS OF PRIMARY EFFICACY VARIABLE(S)

16.1.4.1. Amyloid Removal by Double-Blind Treatment

An MMRM analysis similar to the one described in [Section 16.1.3](#) will be re-run to compare the change during the double-blind period in amyloid PET for participants on gantenerumab (only

Author: █ Version Number: 7
Version Date: 07Dec2023
Template No.: CS_TP_BS016 Revision 6 Reference: CS_WI_BS005
Effective Date: 02Dec2019
Copyright © 2009, 2010, 2012, 2016, 2018, 2019 █ All rights reserved. The contents of this document are confidential and proprietary to █ Holdings Inc. and its subsidiaries. Unauthorized use, disclosure or reproduction is strictly prohibited.

their data in the double-blind period will be included) with the change from the OLE baseline for participants (only their data in the OLE period will be included) on solanezumab or placebo in the double-blind period using an MMRM model.

16.1.4.2. Amyloid Removal by CDR Global Status

The analysis described in [Section 16.1.3](#) will be re-run with the OLE baseline CDR Global (in categories of baseline CDR=0 and baseline CDR >0) as a covariate to estimate the treatment effect for the subgroup Figures of model estimated mean over time or spaghetti plots of individual data over time/EYO (CDR=0 vs CDR >0) will be presented as deemed necessary by Washington University team and may be included in CSR as needed.

16.1.4.3. Gantenerumab Treatment Effects during the Whole Study Duration (Double-Blind + OLE)

To evaluate the treatment effect of gantenerumab during the whole study duration, the change from the double-blind baseline for subjects in the All Gant exposure mITT and for subject in the OLE Gant All Gant exposure mITT will be calculated for each post double-blind baseline visit and will be analyzed using the MMRM model (without controls) described in [Section 16.1.3](#). The MMRM model will include the double-blind baseline value, the double-blind treatment arm (gantenerumab, solanezumab, placebo) as applicable per analysis population, visit, and the interaction between the double-blind treatment arm and visit as the fixed effects. The visit variable will be considered as categorical with the following categories: visit 1 (the ~1-year visit in the double-blind period), visit 2 (the ~2-year visit in the double-blind period), visit 3 (the ~4-year visit in the double-blind period), visit 4 (the OLE baseline visit), visit 5 (the ~1-year OLE visit), visit 6 (the ~2-year OLE visit), visit 7 (the ~3-year OLE visit). Subjects on gantenerumab or placebo during the double-blind period will contribute to all visits. Subjects on solanezumab during the double-blind period will not contribute to post-baseline values within the double-blind period. An unstructured variance-

covariance matrix will be used to model the within-subject errors among the repeated measures. If the unstructured covariance structure matrix results in a lack of convergence, the following covariance structures will be assumed in sequence: heterogeneous Toeplitz, heterogeneous autoregressive, heterogeneous compound symmetry, and compound symmetry. In the case that a structured variance-covariance matrix is used to enable the model to converge, the "sandwich" estimator of the variance-covariance matrix will be employed by using the "empirical" option in the proc mixed procedure.

The corresponding p-value for the difference from no change from baseline and the 95% confidence interval for the estimated least squares mean change at each visit will be presented.

The model described above will also be analyzed with the addition of the double-blind baseline CDR status (CDR=0 vs CDR >0) as a covariate, the two-way interactions of CDR status and the double-blind baseline PiB-PET SUVR, CDR status and treatment arm, and CDR status and visit, and the three-way interaction of CDR status, treatment arm and visit. If the model fails to converge, the model will be removed.

Figures of model estimated mean over time by the double-blind treatment arms or spaghetti plots of individual data over time/EYO by the double-blind treatment arms will be presented as deemed necessary by Washington University team and may be included in CSR as needed.

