3. All Gant exposure mITT: Any subjects treated with Gantenerumab in either DB or OLE who meet mITT criteria using the baseline associated with the first period of Gantenerumab exposure as the baseline reference point. Refer to figure below where the data contributing to the population is highlighted in yellow (and denoted with 'Tx') any period of planned gantenerumab treatment, regardless of double-blind treatment, with controls (further described in [Section 5.4](#)) highlighted in green from both placebo double-

Author: [REDACTED]

Version Number:

7

Version Date:

[figure not shown]
07Dec2023

Template No.: CS_TP_BS016 Revision 6

Reference: CS_WI_BS005

Effective Date: 02Dec2019

blind only subjects and matched controls from DIAN-OBS.

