16.2.3.5. Primary Analysis of CSF Amyloid Beta1-42/40

To evaluate if treatment with gantenerumab increases CSF Amyloid Beta1-42/40, the MMRM as described in [Section 16.2.3.4](#) will be applied for the OLE Gant mITT and the MMRM as described in [Section 16.1.4.3](#) will be applied for the All Gant exposure mITT, with both asymptomatic and symptomatic subjects included within the same model.

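### SAP 16.1.4.3 measures former placebo and solanezumab participants from the double-blind baseline, so its p-values in those arms either contain no gantenerumab or mix its effect with earlier years without it

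*SAP*

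**What the plan says.** SAP 16.1.4.3 gives its purpose as "To evaluate the treatment effect of gantenerumab during the whole study duration". The outcome is "the change from the double-blind baseline for subjects in the All Gant exposure mITT" (and for the OLE Gant All Gant exposure mITT). The fixed effects are the double-blind baseline value, "the double-blind treatment arm (gantenerumab, solanezumab, placebo) as applicable per analysis population", visit, and the arm-by-visit interaction. There are no controls. Visits 1-3 are the double-blind visits at about 1, 2 and 4 years, visit 4 is the OLE baseline, and visits 5-7 are OLE years 1-3.

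On who supplies data: "Subjects on gantenerumab or placebo during the double-blind period will contribute to all visits". And: "Subjects on solanezumab during the double-blind period will not contribute to post-baseline values within the double-blind period". Solanezumab participants therefore enter at visit 4, still as change from the double-blind baseline. The reported result is "The corresponding p-value for the difference from no change from baseline" with a 95% confidence interval at each visit.

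Two other places describe the population or the analysis differently:

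- SAP 5.3 defines the All Gant exposure mITT "using the baseline associated with the first period of Gantenerumab exposure as the baseline reference point". For former placebo and solanezumab participants that is the OLE baseline.
- SAP Section 17, Table B, gives the objective of 16.1.4.3 only for participants who had gantenerumab in the double-blind period.

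The model is reused. In SAP 16.2.3.5, after an OLE-baseline MMRM for the OLE Gant mITT, the 16.1.4.3 model "will be applied for the All Gant exposure mITT, with both asymptomatic and symptomatic subjects included within the same model". SAP 16.2.5 sends the remaining fluid biomarkers to the models of 16.2.3.5.

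**The concern.** A per-visit test of zero change estimates a gantenerumab effect only if the reference point is the start of gantenerumab. That is true of the double-blind gantenerumab arm, apart from the off-drug gap between periods. It is not true of the other two arms, which reach the OLE baseline after years on placebo or on a different antibody.

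Their p-values are nevertheless produced in a section whose stated aim is the effect of gantenerumab. Some would describe a course with no gantenerumab in it. The rest would describe a sum in which earlier change and OLE change may pull in opposite directions, so real plaque removal could show as little or no change. The same ambiguity carries into one of the two primary models for a key secondary variable, CSF Abeta42/40.

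**Working it through.** **1. What each p-value contains in the two crossover arms**

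| Visit | Former placebo | Former solanezumab |
|---|---|---|
| 1-3 (double-blind) | no gantenerumab | no data used |
| 4 (OLE baseline) | no gantenerumab | no gantenerumab |
| 5-7 (OLE years 1-3) | earlier years plus OLE effect | earlier years plus OLE effect |

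This follows from the definitions alone and needs no assumed number.

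**2. The plan's own power figures reproduce.** Protocol Appendix 3, Sections 4.1.2 and 4.1.3, project a 3-year change from the OLE baseline of at least -0.473 (SD 0.540), with 60 to 90 enrolled, 5% annual dropout, and a one-sided one-sample t-test at 0.025.

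- Completers: 60 × 0.95³ = 51.4 and 90 × 0.95³ = 77.2, matching 51 to 77.
- Power for -0.473 at n = 51: 99.998%, matching the stated figure of over 99%.
- Power for -0.22 at n = 51: 81.4%, matching the stated figure of more than 80%.

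No power is stated for 16.1.4.3.

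**3. Tested mean at OLE Year 3 in a crossover arm.** With untreated growth g per year over T pre-OLE years:

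tested change = -0.473 + g × T

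T = 4 to 7 is the double-blind duration in Protocol Appendix 3, Section 1.9.2; SAP 5.4.4 says the two baselines differ by over four years for former placebo participants. The documents give no g. Protocol Appendix 3, Section 1.5.2.2, supports only the direction (amyloid grows in these carriers). The values of g are assumed.

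| g (SUVR/yr) | T = 4 | T = 7 |
|---|---|---|
| 0.02 | -0.473 + 0.08 = -0.393 | -0.473 + 0.14 = -0.333 |
| 0.05 | -0.473 + 0.20 = -0.273 | -0.473 + 0.35 = -0.123 |
| 0.10 | -0.473 + 0.40 = -0.073 | -0.473 + 0.70 = +0.227 |

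The tested change reaches zero at g = 0.473/4 = 0.118 for T = 4, and at g = 0.473/7 = 0.068 for T = 7.

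**4. Power within an arm, same illustration.** The double-blind arms had 52 gantenerumab, 52 solanezumab and 40 placebo carriers, 144 in all (Protocol 3.3). Assuming OLE enrolment in proportion and 5% annual dropout, Year 3 numbers are 14 to 21 for placebo (60 × 40/144 × 0.95³ = 14.3; 90 × 40/144 × 0.95³ = 21.4) and 19 to 28 for solanezumab (60 × 52/144 × 0.95³ = 18.6; 90 × 52/144 × 0.95³ = 27.9). The test is a two-sided 5% one-sample t with SD 0.540.

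| Year 3 test of removal | n = 14 | n = 19 | n = 21 | n = 28 |
|---|---|---|---|---|
| From OLE baseline (-0.473) | 85.7% | 95.0% | 96.8% | 99.4% |
| From double-blind baseline, g = 0.02, T = 4 (-0.393) | 71.2% | 85.1% | 88.7% | 96.0% |
| From double-blind baseline, g = 0.05, T = 4 (-0.273) | 41.8% | 55.0% | 59.7% | 73.2% |

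At visit 4, before any gantenerumab in these arms, the same inputs give p < 0.05 with probability 8-12% at g = 0.02 and 25-47% at g = 0.05. A small p-value there would reflect growth, or solanezumab.

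**5. The right contrast is already in the model.** The baseline covariate has no interaction with visit, so within an arm it cancels in the difference between two visit means. Visit 5, 6 or 7 minus visit 4 is then the change from the OLE baseline. The SAP does not ask for it. Confidence intervals printed separately for visits 4 and 7 do not give an interval for their difference, because the two means come from the same people.

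**The case against.** The strongest reply is that the question is answered elsewhere, and this largely stands. The primary analysis (SAP 16.1.3) tests change from the OLE baseline in all OLE participants. SAP 16.1.4.1 models OLE-only change for former solanezumab and placebo participants together. The first CSF Abeta42/40 model also starts at the OLE baseline. A reader might infer that a real effect in crossover participants could be lost from the plan. It could not; what is missing is an arm-specific test in this model.

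The whole-study baseline may also be deliberate. Protocol Appendix 3, Section 1.9.2, lists summing gantenerumab's biomarker effect over both periods among the OLE objectives, and SAP 5.3 uses the first-exposure baseline to decide who qualifies. That explains the choice for the double-blind gantenerumab arm, the only arm Table B names. It does not explain efficacy p-values in the others.

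Three stronger readings are tempting and are not supported:

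- That no p-value in these arms bears on gantenerumab. This holds before crossover. At visits 5-7, if untreated amyloid rises, a significant fall below the double-blind baseline is conservative evidence of removal.
- That the sign would reverse. No growth rate is documented; at an assumed 0.10 per year the sign changes over seven years but not over four.
- That the interim CSF results depend on this model. Section 17 runs only the first model in a section unless stated otherwise, and in 16.2.3.5 that is the OLE-baseline one.

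The section also carries no decision rule, and SAP 7.4 makes no multiplicity adjustment, so the consequence is one of interpretation.

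**Conclusion.** The point holds for the double-blind placebo and solanezumab arms of 16.1.4.3 and for the second CSF Abeta42/40 model in 16.2.3.5. Pre-crossover p-values there do not test gantenerumab. At visits 5-7 the tested quantity is a net change: a significant fall in amyloid would be conservative if untreated amyloid rises, but a null or positive result would have no clear meaning. For solanezumab the earlier years were on another drug, so even the direction of the earlier change is an assumption. The wording also disagrees with the population's own baseline in 5.3 and with Table B.

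This is a definitional fault and does not depend on any growth rate. The figures are illustrative. They rest on assumed growth, on a pooled projection (which includes participants already on gantenerumab) applied to each crossover arm, on an SD of 0.540 carried over to a longer interval, and on proportional enrolment. Year 3 data may also be sparse, since the SAP revision history records that the OLE ended early.

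**What to change.** Keep the model and make four changes to the text:

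- For the double-blind placebo and solanezumab arms, prespecify the within-arm contrasts of visits 5, 6 and 7 minus visit 4 as the gantenerumab-effect tests, with confidence intervals.
- Keep change from the double-blind baseline as the gantenerumab-effect test only for the double-blind gantenerumab arm, in line with Table B.
- Present placebo visits 1-4 and solanezumab visit 4 as a descriptive pre-gantenerumab course, without efficacy p-values.
- Apply the same rule where 16.2.3.5 reuses the model, and to the fluid biomarkers that 16.2.5 routes through it.

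The cost is a few lines of SAP wording and an extra ESTIMATE or LSMESTIMATE statement. No new data are needed, and the primary analysis does not change.
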